6.8 Prior and Concomitant Treatment

6.8.1 Prior Treatment

Prior therapies (including prescription and non-prescription, herbal, and alternative therapies) that were being taken/used from 21 days prior to first dose of study treatment

through the end of SFU period will be collected. Antibiotic therapy for the previous 3 months from first dose of study treatment will also be collected. For all prior therapies not taken for SCLC, collect therapy name, indication, dose, unit, frequency, route, start and stop dates.

All prior cancer treatment therapies will be collected.

Prior therapies taken for SCLC dating back to initial diagnosis will be collected. For all prior therapies taken for SCLC (eg, chemotherapy, immunotherapy, biological therapy, or targeted therapy), the following information should be collected (in the order they were administered):

- therapy name
- indication
- dose and schedule of the agent(s)
- unit
- frequency
- start and stop dates
- best response
- **best response date**
- disease stage in which it was administered
- reason for discontinuation (disease progression, clinical progression, toxicity, subject's decision, completion of treatment)
- **date of progression**

Additionally, details of the dates, portals, and total administered dose by portal should be recorded for all courses of radiation therapy, including those directed at the primary and metastatic site(s). Details of prior radioisotope therapy should also be recorded.

6.8.2 Concomitant Treatment

Throughout the study, investigators may prescribe any concomitant medications or treatments deemed necessary to provide adequate supportive care except for those listed in Section 6.1.7

Concomitant therapies (including prescription and non-prescription, herbal, and alternative therapies) are to be collected from main study informed consent through the end of SFU period. **Start and stop time should also be recorded for therapies taken for CRS and ICANS.**

For anticancer therapies consisting of multiple individual components, information for each component should be collected. For other (not taken for the disease under study)

concomitant therapies (including vaccines), collect therapy name, indication, dose, unit, frequency, start and stop dates.

Vaccines

Every effort should be made to complete any planned vaccinations prior to study treatment. Refer to Section [5.2](#) for details and restrictions prior to first dose of study treatment. The use of vaccines (except live and live-attenuated vaccines) may be allowed during study treatment (refer to Section [6.1.6](#) for details). In the event where a patient requires steroids for treatment of adverse events, vaccination should be avoided while on steroids.

7. Discontinuation of Study Treatment and Subject Discontinuation/Withdrawal

Subjects have the right to withdraw from investigational product and/or non-investigational products(s)/auxiliary medicinal product(s), protocol procedures, or the study as a whole at any time and for any reason without prejudice to their future medical care by the physician or at the institution.

The investigator and/or sponsor can decide to withdraw a subject(s) from investigational product, device, and/or noninvestigational products(s)/auxiliary medicinal product(s), protocol procedures, or the study as a whole at any time prior to study completion for the reasons listed in Section [7.1](#) and Section [7.2.1](#).

7.1 Discontinuation of Study Treatment

Subjects (or a legally authorized representative) can decline to continue receiving investigational product and/or noninvestigational products(s)/auxiliary medicinal product(s) and/or procedures at any time during the study but continue participation in the study. If this occurs, the investigator is to discuss with the subject the appropriate processes for discontinuation from investigational product or noninvestigational products(s)/auxiliary medicinal product(s) and must discuss with the subject the possibilities for continuation of the Schedule of Activities (see Section [1.3](#)) including different options of follow-up (eg, in person, by phone/mail, through family/friends, in correspondence/communication with other treating physicians, from the review of medical records) and collection of data, including endpoints, adverse events, and product complaints (including device-related adverse events, as applicable) and must document this decision in the subject's medical records. Subjects who have discontinued investigational product and/or noninvestigational products(s)/auxiliary medicinal product(s) and/or procedures should not be automatically removed from the

study. Whenever safe and feasible, it is imperative that subjects remain on-study to ensure safety surveillance and/or collection of outcome data. **At minimal vital status (survival status) should be collected, through as an example, direct or family member contact or family members contact or through the attending physician or medical records, public registries, and public records, subject to local laws and regulations.**

Reasons for early removal from protocol-required investigational product(s), non-investigational products(s)/auxiliary medicinal product(s), or procedural assessments may include any of the following:

- decision by sponsor
- lost to follow-up
- death
- adverse event
- subject request
- ineligibility determined
- protocol deviation
- non-compliance
- disease progression
- requirement for alternative therapy
- pregnancy

7.2 Subject Discontinuation/Withdrawal From the Study

Withdrawal of consent for a study means that the subject does not wish to receive further investigational product(s) and/or noninvestigational product(s)/auxiliary medicinal product(s) or procedures, and the subject does not wish to or is unable to continue further study participation. Subject data up to withdrawal of consent will be included in the analysis of the study, and where permitted, publicly available data can be included after withdrawal of consent. **The subject is not considered to have ended the study until there is no means to continue collection of vital status (survival status).** The investigator is to discuss with the subject appropriate procedures for withdrawal from the study and must document the subject's decision to withdraw in the subject's medical records. Subjects who are withdrawn or removed from treatment or the study will not be replaced.

If a subject withdraws from the study, they may request destruction of any samples taken and not tested, and the investigator must notify Amgen accordingly (see

Section 11.6 for further details). Refer to the Schedule of Activities (Section 1.3) for data to be collected at the time of study discontinuation and follow-up and for any further evaluations that need to be completed.

7.2.1 Reasons for Removal From Study

Reasons for removal of a subject from the study are:

- decision by sponsor
- withdrawal of consent from study
- death
- lost to follow-up

7.3 Lost to Follow-up

A subject will be considered lost to follow-up if they repeatedly fail to return for scheduled visits and is unable to be contacted by the study site.

The following actions must be taken if a subject fails to return to the clinic for a required study visit:

- The site must attempt to contact the subject and reschedule the missed visit as soon as possible and counsel the subject on the importance of maintaining the assigned visit schedule and ascertain whether or not the subject wishes to and/or is able to continue in the study.
- In cases in which the subject is **at risk to be** lost to follow-up, where permitted per local regulation, the investigator or designee must make every effort to regain contact with the subject.
- **The investigator or designee should attempt** 3 telephone calls and, if necessary, a certified letter to the subject's last known mailing address or local equivalent methods [contact the patient's family or direct assigned contact]). These contact attempts are to be documented in the subject's medical record.
- **The investigator should contact the subject's attending physician.**
- If the subject continues to be unreachable **or vital status (survival status) cannot be obtained through any of the above actions**, they will be considered to have withdrawn from the study with a primary reason of lost to follow-up.
- For subjects who are lost to follow-up, the investigator should search publicly available records where permitted to ascertain **vital status** (survival status). This ensures that the data set(s) produced as an outcome of the study is/are as comprehensive as possible.

8. Study Assessments and Procedures

Study procedures and their time points are summarized in the Schedule of Activities (Section 1.3).

If an enrolled subject is subsequently determined to be ineligible for the study, this must be discussed with the sponsor immediately upon occurrence or awareness to determine if the subject is to continue or discontinue study treatment.

Adherence to the study design requirements, including those specified in the Schedule of Activities (Section 1.3), is essential and required for study conduct.

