8.4.4 Vital Status (Survival Status)

Vital status (survival status) must be obtained for all subjects within the limits of local law (see Section 7.1 and Section 7.2). This includes subjects who may have discontinued study visits with or without withdrawing consent and should include interrogation of public databases, if necessary. If deceased, the date and reported cause of death should be obtained.

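### Section 7.3 closes an unreachable subject as lost to follow-up even when survival can still be learned from family, physician or chart, contradicting Section 7.2; later deaths may be missed

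*Protocol*

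**What the plan says.** Protocol Section 7.3 opens with a definition that rests on contact only: repeated missed visits together with the site's inability to reach the subject. It then lists what the site must do: attempt to contact the subject and reschedule, make telephone calls, send a letter or use local equivalents such as family contact, and approach the treating doctor ("The investigator should contact the subject's attending physician"). The closing rule then applies to anyone still out of reach "or vital status (survival status) cannot be obtained through any of the above actions"; in that event "they will be considered to have withdrawn from the study with a primary reason of lost to follow-up". Only after that does the section say, of subjects already given this label, that "the investigator should search publicly available records where permitted to ascertain" whether they are alive.

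Three other parts of the protocol bear on the same subject:

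- Section 7.2: "The subject is not considered to have ended the study until there is no means to continue collection of vital status (survival status").
- Section 8.1.5 runs long-term survival follow-up every 12 weeks by telephone, clinic visit or chart review.
- Section 8.4.4 requires vital status for all subjects within local law. "This includes subjects who may have discontinued study visits with or without withdrawing consent", and public databases are to be used if necessary.

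Section 7.2.1 lists lost to follow-up among the reasons for removal from the study.

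**The concern.** Section 7.3 is the checklist that a site coordinator will use when a subject stops responding. Its closing rule uses *or* where the rest of the protocol needs *and*. A coordinator who cannot reach the subject, but has just heard from the attending physician that the subject is alive, may close that subject under 7.3 and be compliant with it. The same act breaches Section 7.2.

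The rule governs capture of the primary endpoint. If survival follow-up lapses at closure, a later death may not be recorded. Becoming unreachable may well be related to decline, although the documents give no data on this. The trial is open-label, so the tendency to drop out of contact could differ between arms.

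**Working it through.** **Logic check.** Let A = subject unreachable and B = vital status not obtainable by the listed actions.

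| Case | 7.3 as written (A or B) | 7.2 | 7.3 with *and* |
|---|---|---|---|
| A true, B true | withdrawn | ended, if no other means is left | withdrawn |
| A true, B false | withdrawn | not ended | stays in survival follow-up |
| A false, B false | stays | not ended | stays |

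The conflict is the second row. It is not an empty case: family and physician contact are among the listed actions, so B can be false while A is true. It also clashes with Section 8.1.5, where chart review is a valid way to follow survival and needs no contact with the subject. The lead sentence of 7.3 has the same defect, since it does not mention vital status.

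**Order of steps.** Section 7.2 asks whether any means of collecting vital status remains. That cannot be answered before medical records and public records have been tried. In 7.3 the public-record search follows the declaration, so it is not one of the actions above it. Medical-record review, which Section 7.1 names as a source after treatment discontinuation, does not appear in 7.3. Where public records are closed, 7.3 offers the site no further route after the label.

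**What still protects OS.** Section 8.4.4, the post-label search in 7.3 and the ad hoc survival collection in Section 4.1 all remain in force. The documents supplied contain no rule that discards a death found after the label. The SAP supplied is an integrated safety plan and has no OS censoring rules.

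**Size.** The protocol redacts sample size, events, target HR, control median and dropout, so there is no figure to reproduce. The following is illustrative only.

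Assumptions: 250 per arm, control median 10 months, true HR 0.70, 12-month uniform accrual, cutoff at 20 months, exponential survival, unstratified log-rank test at two-sided 0.05. A share p of an arm's deaths is missed, each such subject being censored a mean of 1.5 months before death. With a short lead the risk sets barely change, so

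observed HR ≈ true HR × (1 − p_tarlatamab) / (1 − p_SOC).

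For 5% (SOC) and 2% (tarlatamab): 0.70 × 0.98 / 0.95 = 0.722. With the arms reversed: 0.70 × 0.95 / 0.98 = 0.679. Simulation (4,000 replicates per row) agrees:

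| Deaths missed, SOC / tarlatamab | Formula HR | Simulated HR | Power |
|---|---|---|---|
| 0% / 0% | 0.700 | 0.700 | 84% |
| 5% / 5% | 0.700 | 0.699 | 82% |
| 5% / 2% | 0.722 | 0.720 | 76% |
| 8% / 2% | 0.746 | 0.742 | 67% |
| 2% / 5% | 0.679 | 0.678 | 88% |
| 2% / 8% | 0.657 | 0.659 | 92% |
| 5% / 2%, with 80% of these deaths recovered | 0.704 | 0.705 | 81% |

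For the last row, 5% and 2% shrink to 1% and 0.4%: 0.70 × 0.996 / 0.99 = 0.704. With the cutoff set instead at an assumed 260 observed deaths, the HR is 0.722 for 5% / 2% and 0.678 for 2% / 5%. An event-driven trigger therefore restores the event count but not the HR.

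**The case against.** The strongest reply is that the protocol, taken as a whole, already requires the right thing. Section 8.4.4 makes vital status mandatory within local law, including for subjects who have stopped visits. Section 7.1 sets the same minimum after treatment stops ("At minimal vital status (survival status) should be collected, through as an example, direct or family member contact", among other sources). Section 7.2 says when a subject has ended the study. For harm to occur, a site must obtain survival from the physician, record the subject as lost anyway, and then overlook those sections. One can also read the phrase about the listed actions as qualifying *unreachable*, so that family contact counts as reaching the subject. On that view the matter is one of tidying.

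Much of this stands. A reader might infer that such deaths drop out of the primary OS analysis, or that 12-weekly survival contact stops at the label. The documents say neither, and 7.3 itself continues the search afterwards. A reader might also take one direction of HR bias as the expected one. The loss rates, the difference between arms and the lead time have no source in the documents, the direction can reverse, and recovery of most of these deaths removes most of the effect.

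The textual conflict survives the reply. The generous reading does not repair the lead sentence, which turns on contact by the site alone, and it does not cover a subject whose survival is known only from the physician or chart. A general duty in 8.4.4 does not tell a site to disregard a specific closing rule in 7.3.

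**Conclusion.** The closing rule in Section 7.3 is wrong as written. It contradicts Section 7.2 and fits badly with Sections 8.1.5 and 8.4.4, and this rests on the text alone. The consequence is a risk that some later deaths are missed, chiefly where a site follows 7.3 in isolation and public records cannot be searched. It is not a demonstrated loss from OS.

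The size cannot be derived from the documents. Under the assumptions above, missing 5% of deaths in both arms leaves the HR unchanged and costs about 2 points of power (84% to 82%), or delays an event-driven analysis. Unequal loss of 2% against 5% to 8% with no recovery moves a true HR of 0.70 to anywhere from about 0.66 to 0.74, depending on which arm loses more. With 80% recovery, the 5% / 2% case shifts the HR by only about 0.005. The study-level handling of deaths found after loss to follow-up is not in the documents supplied, so no claim is made about it. The correction is worth making because it concerns the primary endpoint and costs almost nothing.

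**What to change.** Amend Section 7.3 in four respects:

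1. Replace *or* with *and* in the closing rule, so that only a subject who is unreachable and whose vital status cannot be obtained by any route is recorded as lost to follow-up.
2. Align the lead sentence with Section 7.2, so that failed contact alone does not define loss to follow-up.
3. List medical-record review and the public-record search (where permitted) among the actions completed before the declaration. The later search for subjects already declared lost can stay as well.
4. State, with a cross-reference to Section 8.4.4, that an unreachable subject whose vital status can be obtained remains in 12-weekly survival follow-up.

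The cost is a few sentences in an amendment, which a site memo could cover in the meantime. It needs no new visits or data sources, since Section 7.1 already names these channels. Sites should also review subjects already recorded as lost to follow-up and resume survival follow-up where a source exists.

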8.1 General Study Periods

8.1.1 Screening, Enrollment, and/or Randomization

Screening:

The main study informed consent must be obtained before completing any screening procedure with the following exceptions:

- assessments that were performed as SOC prior to signature of informed consent, but within the protocol specified window (a maximum of 21 days prior to randomization) can be used as screening assessments and do not need to be repeated to confirm subject eligibility
- discontinuation of standard therapy for any disallowed therapy

After the subject has signed the main ICF, the site will register the subject as screened in the IRT in order to assess eligibility for participation. The screening window (including randomization in IRT for eligible subjects) is up to 21 days from the date of signing the main study informed consent.

All screening evaluations must be completed and reviewed to confirm that potential subjects meet all eligibility criteria prior to randomization. The investigator will maintain a screening log to record details of all subjects screened and to confirm eligibility or record reasons for screening failure, (see Section 5.5) as applicable.

If a subject has not met all eligibility criteria at the end of the screening period **and prior to randomization**, the subject will be registered in IRT as a screen fail. Screen fail subjects may be eligible for rescreening up to 2 times at the discretion of the investigator, after consultation with the Amgen Medical Monitor.

Rescreen subjects must first be registered as screen failures in IRT and subsequently registered as rescreens. Once the subject is registered as rescreened, a new 21-day screening window will begin. Subjects will retain the same subject identification number previously assigned. Subjects rescreening within 21 days of the signing of the original main study informed consent need to repeat the assessment(s) that did not originally meet the eligibility criteria and ensure all other eligibility criteria are still met prior to enrollment and study assessments are still valid and within the screening window (ie,

imaging scans, local labs, etc.). If the rescreening period begins more than 21 days after the original signing of the main study ICF, all screening procedures (except the 3 exceptions mentioned above), including informed consent, must be repeated.

8.1.2 Treatment Period

Visits will occur per the Schedule of Activities ([Section 1.3](#)). For tarlatamab, on-study cycle 1 visits may be completed within \pm 1 day, cycle 2 visits have a \pm 2-day window, and all subsequent visits beginning in cycle 3 will have a \pm 3-day window, unless otherwise specified (Note: the treatment window for SOC therapies is based on regional prescribing information). Day 1 should occur on the day of randomization wherever possible, however day 1 can occur up to end of the third calendar day from randomization, if needed, due to logistical reasons. All subsequent doses and study visits will be scheduled based on the day 1 date. Administration of investigational product(s) and/or noninvestigational product(s)/auxiliary medicinal product(s) is to be administered last during each visit that it is required.

8.1.3 End of Treatment

Upon permanent discontinuation from study treatment for any reason, an End of Treatment (EOT) visit will be performed as soon as possible (within 14 days) after last dose and prior to start of subsequent anti-cancer therapy. **If a subject is unable to attend the EOT visit, the subject at minimum should be followed via telephone, clinic visit, or chart review to assess for survival and the commencement of subsequent cancer therapy.**

8.1.4 Safety Follow-up

Upon permanent discontinuation from the study treatment for any reason, an SFU visit will be performed approximately **60** (+ 5) days after the last dose of study treatment, even if subsequent anti-cancer therapy has been initiated within that period. **If a subject is unable to attend the SFU visit, the subject at minimum should be followed via telephone, clinic visit, or chart review to assess for survival and the commencement of subsequent cancer therapy.**

8.1.5 Long-term Follow-up

Following the SFU visit, there will be an LTFU period for clinical evaluation of disease status and survival. Subjects will be followed via telephone, clinic visit, or chart review to assess for survival and/or the commencement of subsequent cancer therapy every 12 weeks (\pm 14 days) from the SFU visit (or last imaging visit, whichever is later) for up

to 3 years after the last subject is enrolled, or 1 year from the subject's last dose of study treatment, whichever is later.

Vital status (survival status), imaging and tumor assessment (until radiographic disease progression), subsequent anticancer treatment (ie, subsequent therapies taken for SCLC), serious adverse events suspected to be related to study treatment, and urine pregnancy test **60** days after last dose of tarlatamab will be collected.

The assessments that will be collected during the LTFU are designated in the Schedule of Activities (Section 1.3).

8.1.6 End of Study

Refer to Section 4.5 for the end of study definition. The end of study visit is the last visit shown in the Schedule of Activities (Section 1.3) which is the final LTFU visit.

